6.1.1.2. Sensitivity and Supplemental Analyses

Sensitivity analyses will be performed to the primary efficacy endpoint:

The primary efficacy analyses will also be conducted using the PP population as supplemental analyses.

The primary endpoint will also be analyzed in which participants who discontinued the study before Day 28 without event will be censored at Day 25.

For sensitivity analysis of primary endpoint, Cox proportion hazard models with terms including treatment and treatment strata (ie, region, vaccination, baseline serology, baseline viral load $<10^4$ copies/mL vs $\geq 10^4$ copies/mL). These factors will be used to estimate the hazard ratio (the ratio of alleviation of all targeted signs and symptoms) and its 95% CI. Additional analyses may be performed adjusting for baseline covariates (such as age, gender, etc) as additive terms to the primary model, if necessary.

Based on FDA request, a sensitivity analysis excluding participants only from Site 1488 will be conducted as well.

6.2. Secondary Endpoint(s)

6.2.1. Incidence of Treatment-Emergent Adverse Events (TEAEs)

The incidence of TEAEs will be summarized by treatment group, by system organ class (SOC) and preferred term (PT) using the SAS population.

6.2.2. Incidence of SAEs and AEs Leading to Discontinuations

The incidence of SAEs and AEs leading to discontinuation will be summarized by treatment group using the SAS population.

6.2.3. Proportion of Participants with COVID-19 Related Hospitalization or Death From Any Cause Through Day 28

The estimand for proportion of participants experiencing COVID-19 related hospitalization or death from any cause through Day 28 is the difference in proportions of participants experiencing COVID-19 related hospitalization or death from any cause through Day 28 in nonhospitalized adult patients with COVID-19 who are at low risk of progression to severe disease and were treated ≤ 5 days after COVID-19 symptom onset. This will be estimated irrespective of adherence to randomized treatment.

The statistical methodology for proportion of participants with COVID-19 related hospitalization or death from any cause through Day 28 will be as follows:

The cumulative proportion of participants hospitalized for the treatment of COVID-19 or death during the first 28 days of the study will be estimated for each treatment group using the Kaplan-Meier method to take account of lost to follow-up and summarized graphically for each treatment group. The estimand is the difference of the proportions in the 2 groups and its 95% CI will be presented, as well as, the associated two sample proportion test (Wald test results). For the 95% CI, the corresponding estimate of the standard error is computed using Greenwood's formula⁴. The Greenwood's formula to estimate the variance of the difference of proportions at Day 28 is $[\text{Var}(S_{PF}(28)) + \text{Var}(S_{\text{Placebo}}(28))]$. Instead of dealing with $S(t_i)$ the log-log approach to CI will be used. The 95% CI will be computed for the estimate of $L(t) = \log(-\log(S(t)))$, the log hazard function.

The CI will be in the right range when transformed back to $S(t) = \exp(-\exp(L(t)))$. Antilogging this CI will give a 95% confidence interval for the difference itself.

A sensitivity analysis for proportion of participants with COVID-19 related hospitalization or death from any cause through Day 28 will be provided using mITT1 as follows:

For participants with missing data due to lost to follow up for COVID-19 related hospitalization or death from any cause, the sensitivity analysis will implement the following event imputation methodology for those with missing data:

- If the participant's last observed data is prior to Day 21, then impute as an event with event day as day of last observed data +1.
- If the participant's last observed data is on or after Day 21, then no imputation for event will be done and participant remains censored at day of last observed data.

6.2.4. Proportion of Participants with Death (all cause) through Week 24

Descriptive statistics will be used to summarize proportion of death through Week 24 by treatment group using mITT1 populations. Treatment comparisons between groups will be presented as odds ratios with 95% confidence intervals and P-value based on logistic regression model (if data permit).

If zero counts are observed in either treatment group, the Fishers Exact test will be performed (instead of logistic regression) and p-value provided.

The participants enrolled under or after protocol amendment 6 will not include this summary.

6.2.5. Number of COVID-19 Related Medical Visits through Day 28

The number of COVID-19 related medical visits will be analyzed with a negative binomial regression model, using the log total number of days of data collection as the participant offset variable (if data permit). The resulting analysis will evaluate the difference in estimated rate of number of medical visits between treatment groups and the associated 95% CI. The analyses will be done using mITT1 populations.

6.2.6. Number of Days of Hospital and ICU Stay in Participants with COVID-19 Related Hospitalization

Health resource utilization data will be summarized by treatment group for each treatment. The analyses will be done using mITT1 populations. Descriptive statistics (ie, mean, median, range) will be used to summarize this endpoint.

The resulting analysis will provide the estimated difference in the average of number of days stayed in the hospital between treatment groups, with p-value and 95% confidence interval. The analyses will be done using the mITT1 population.

6.2.7. Proportion of Participants with Severe Signs/symptoms Attributed to COVID19 through Day 28

Participants will record a daily severity rating of their symptom severity over the past 24 hours based on a 4-point scale in which 0 is reported if no symptoms were present; 1 if mild; 2 if moderate; and 3 if severe. A participant with severe score for any targeted symptoms post-baseline will be counted as severe.

Vomiting and diarrhea will each be rated on a 4-point frequency scale where 0 is reported for no occurrence, 1 for 1 to 2 times, 2 for 3 to 4 times, and 3 for 5 or greater. Sense of smell and sense of taste will each be rated on a 3-point Likert scale where 0 is reported if the sense of smell/taste was the same as usual, 1 if the sense of smell/taste was less than usual, and 2 for no sense of smell/taste.

The proportion of participants with any severe targeted signs/symptoms attributed to COVID-19 through Day 28 will be summarized by treatment group. Observed proportions for each targeted signs and symptom with severe category only will be plotted over time through Day 28. Additionally, observed proportion of participants reporting the presence of each targeted sign and symptom that is mild, moderate or severe categories will also be presented.

Treatment comparisons between groups will be presented as odds ratios with 95% CI and p-value based on logistic regression model and using the mITT1 population.

To evaluate the severity of signs/symptoms attributed to COVID-19, the following analysis will be performed and treatment comparison between groups will be done using the same statistical method as mentioned above:

- Proportion of participants with any severe (ie, any targeted symptoms with severe baseline score) targeted signs/symptoms attributed to COVID-19 at Day 1 (baseline).
- Proportion of participants with any severe targeted signs/symptoms attributed to COVID-19 Day 2 to Day 6 (during treatment).
- Proportion of participants with any severe targeted signs/symptoms attributed to COVID-19 Day 7 to Day 28 (post treatment).

The above severity endpoint is based on participant daily diary data only. To align the severity of signs and symptoms with the primary and key secondary endpoints, an expanded evaluation of severity of will be assessed to include hospitalization due to COVID-19 and death of any cause in the severity assessment based on CRF data.

An expanded definition severity of signs and symptoms that will include CRF data (hospitalization due to COVID-19 and death of any cause) is defined as follows: Participant with hospitalization due COVID-19 or death of any cause will be considered as having severe signs and symptoms, this definition overrides the observed severity of signs and symptoms from participant diary. To incorporate hospitalization and death in the severity of signs and symptoms, the date of hospitalization and date of discharged will be used. Treatment comparisons between groups for expanded severity will be presented as odds ratios with 95% CI and p-value based on logistic regression model and using the mITT1 population

This analysis will be performed for overall, baseline (Day 1), Day 2 to Day 6 (during treatment) and Day 7 to Day 28 (post treatment).

6.2.8. Time (days) to Sustained Resolution of All Targeted COVID-19 Signs/symptoms through Day 28

The secondary endpoint of time (days) from start of study intervention or placebo (Day 1) until sustained resolution of all targeted COVID-19 associated signs/symptoms will be based on self-assessment.

Sustained resolution is defined as when all targeted symptoms are scored as absent for 4 consecutive days. The first day of the 4 consecutive-day period will be considered the First Event Date.

The censoring method and analysis of time (days) to sustained resolution of all targeted COVID-19 signs/symptoms will be similar to the censoring method and analysis of the primary endpoint. The analysis will be done using mITT1 population.

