7. DISCONTINUATION OF STUDY INTERVENTION AND PARTICIPANT DISCONTINUATION/WITHDRAWAL

7.1. Discontinuation of Study Intervention

It may be necessary for a participant to permanently discontinue study intervention. Reasons for permanent discontinuation of study intervention include the following.

- AE (including Grade 3 severity or greater and considered by the investigator to be related to study intervention);
- SAE considered by the investigator to be related to the study intervention;
- Requirement for prohibited concomitant medication;
- Death;
- Pregnancy;
- Study terminated by sponsor;
- Withdrawal by participant or legally authorized representative
- Hospitalization during the active treatment period;
- Miss more than 2 consecutive doses of study intervention.

Note that discontinuation of study intervention does not represent withdrawal from the study. If study intervention is permanently discontinued, the participant will remain in the study to be evaluated for all subsequent scheduled assessments. See the [SoA](#) for data to be collected at the time of discontinuation of study intervention and follow-up for any further evaluations that need to be completed.

In the event of discontinuation of study intervention, it must be documented on the appropriate CRF/in the medical records whether the participant is discontinuing further receipt of study intervention or also from study procedures, posttreatment study follow-up, and/or future collection of additional information.

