8.1.2. COVID-19-Related Medical Visit Details

Details of participants' COVID-19-related medical visits (ie, hospitalization, practitioner's office, home healthcare services, telemedicine, urgent care, emergency room ≤ 24 hours,

extended care facility stay) will be collected during study visits, including level of care (ICU status) and dates of utilization, including admission and discharge, as applicable.

Hospitalization is defined as >24 hours of acute care, in a hospital or similar acute care facility, including Emergency Rooms or temporary facilities instituted to address medical needs of those with severe COVID-19 during the COVID-19 pandemic. This includes specialized acute medical care unit within an assisted living facility or nursing home. This does not include hospitalization for the purposes of public health and/or clinical trial execution.

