8.3.7. Disease-Related Events and/or Disease-Related Outcomes Not Qualifying as AEs or SAEs

Not applicable.

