8.3.8.1. Lack of Efficacy

The investigator must report signs, symptoms, and/or clinical sequelae resulting from lack of efficacy. Lack of efficacy or failure of expected pharmacological action is reportable to Pfizer Safety **only if associated with an SAE**.

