10.3.1. Definition of AE

AE Definition

• An AE is any untoward medical occurrence in a patient or clinical study participant, temporally associated with the use of study intervention, whether or not considered related to the study intervention.• Note: An AE can therefore be any unfavorable and unintended sign (including an abnormal laboratory finding), symptom, or disease (new or exacerbated) temporally associated with the use of study intervention.

Events Meeting the AE Definition

• Any abnormal laboratory test results (hematology, clinical chemistry, or urinalysis) or other safety assessments (eg, ECG, radiological scans, vital sign measurements), including those that worsen from baseline, considered clinically significant in the medical and scientific judgment of the investigator. Any abnormal laboratory test results that meet any of the conditions below must be recorded as an AE:
• Is associated with accompanying symptoms.• Requires additional diagnostic testing or medical/surgical intervention.• Leads to a change in study dosing (outside of any protocol-specified dose adjustments) or discontinuation from the study, significant additional concomitant drug treatment, or other therapy.• Exacerbation of a chronic or intermittent preexisting condition, including either an increase in frequency and/or intensity of the condition.• New condition detected or diagnosed after study intervention administration, even though it may have been present before the start of the study.• Signs, symptoms, or the clinical sequelae of a suspected drug-drug interaction.• Signs, symptoms, or the clinical sequelae of a suspected overdose of either study intervention or a concomitant medication. Overdose per se will not be reported as an AE or SAE unless it is an intentional overdose taken with possible suicidal/self-harming intent. Such overdoses should be reported regardless of sequelae.

Events **NOT** Meeting the AE Definition

- Any clinically significant abnormal laboratory findings or other abnormal safety assessments that are associated with the underlying disease, unless judged by the investigator to be more severe than expected for the participant's condition.
- The disease/disorder being studied or expected progression, signs, or symptoms of the disease/disorder being studied, unless more severe than expected for the participant's condition.

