10.3.2. Definition of an SAE

An SAE is defined as any untoward medical occurrence that, at any dose, meets one or more of the criteria listed below:

a. Results in death

b. Is life-threatening

The term "life-threatening" in the definition of "serious" refers to an event in which the participant was at risk of death at the time of the event. It does not refer to an event that hypothetically might have caused death if it were more severe.

c. Requires inpatient hospitalization or prolongation of existing hospitalization

In general, hospitalization signifies that the participant has been admitted (usually involving at least an overnight stay) at the hospital or emergency ward for observation and/or treatment that would not have been appropriate in the physician's office or outpatient setting. Complications that occur during hospitalization are AEs. If a complication prolongs hospitalization or fulfills any other serious criteria, the event is serious. When in doubt as to whether "hospitalization" occurred or was necessary, the AE should be considered serious.

Hospitalization for elective treatment of a preexisting condition that did not worsen from baseline is not considered an AE.

d. Results in persistent or significant disability/incapacity
 
• The term disability means a substantial disruption of a person’s ability to conduct normal life functions.• This definition is not intended to include experiences of relatively minor medical significance, such as uncomplicated headache, nausea, vomiting, diarrhea, influenza, and accidental trauma (eg, sprained ankle), that may interfere with or prevent everyday life functions but do not constitute a substantial disruption.

e. Is a congenital anomaly/birth defect

f. Is a suspected transmission via a Pfizer product of an infectious agent, pathogenic or non-pathogenic, is considered serious.
 
The event may be suspected from clinical symptoms or laboratory findings indicating an infection in a participant exposed to a Pfizer product. The terms “suspected transmission” and “transmission” are considered synonymous. These cases are considered unexpected and handled as serious expedited cases by pharmacovigilance personnel. Such cases are also considered for reporting as product defects, if appropriate.

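### SAEs are summarised by arm with no split for COVID-19 admissions, and the protocol does not settle whether those admissions are SAEs, so the efficacy effect could offset other serious events in the overall SAE line

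*SAP*

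**What the plan says.** SAE incidence and AEs leading to discontinuation are secondary safety endpoints (Protocol section 3; SAP 3.2). SAP 6.2.2 gives their analysis in one sentence: "The incidence of SAEs and AEs leading to discontinuation will be summarized by treatment group using the SAS population". By contrast, SAP 6.2.1 specifies for all TEAEs: "The incidence of TEAEs will be summarized by treatment group, by system organ class (SOC) and preferred term (PT) using the SAS population". SAP 6.6.1 restricts TEAE summaries to events starting by Day 34, so the AE window contains the whole Day 28 window of the key secondary efficacy endpoint, COVID-19-related hospitalisation or death from any cause.

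On whether a COVID-19 admission is recorded as an SAE, the protocol gives these texts:

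- Section 8.3.7, headed "Disease-Related Events and/or Disease-Related Outcomes Not Qualifying as AEs or SAEs", contains only a statement that it does not apply.
- Section 10.3.1 lists among events that are not AEs: "The disease/disorder being studied or expected progression, signs, or symptoms of the disease/disorder being studied, unless more severe than expected" for the participant's condition.
- Section 10.3.2 makes an event serious if it "Requires inpatient hospitalization or prolongation of existing hospitalization", and resolves doubt about hospitalisation towards serious.
- Section 8.3.8.1 says: "The investigator must report signs, symptoms, and/or clinical sequelae resulting from lack of efficacy".

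Section 7.1 lists "Hospitalization during the active treatment period" among the reasons for stopping study intervention, as an item separate from AE and SAE.

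**The concern.** The efficacy endpoint and the safety endpoint may count the same events. If COVID-19 admissions enter the SAE count and the drug prevents them, the drug arm shows fewer SAEs for reasons unrelated to tolerability. A real excess of other serious events on drug could then be offset in the total.

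The recording rule adds to the problem. Sections 8.3.7, 10.3.2 and 8.3.8.1 lean towards recording a COVID-19 admission as an SAE. Section 10.3.1 allows it to be left out when the investigator regards it as expected progression. Two sites could follow the text and record the same admission differently, and SAP 6.2.2 gives no means of telling the two kinds of event apart afterwards. SAP 6.6.2 repeats SAEs by vaccination status, so the same question carries into that table.

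**Working it through.** **Inputs from the documents**

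- First interim (Protocol 2.2.2): 2 of 333 on drug and 8 of 329 on placebo hospitalised, no deaths.
- Sample size (Protocol 9.5; SAP 2.3): 26 total endpoint events, a 70% reduction, 1880 participants before the dropout allowance, randomised 1:1, so 1880/2 = 940 per arm.

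**The plan's own figures.** 2/333 = 0.6% and 8/329 = 2.4%, as stated.

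**Gap from efficacy alone, if every endpoint event is recorded as an SAE**

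- First interim: 2.43% − 0.60% = 1.83 points. Extra SAEs on drug that would level the arms: 8 × 333/329 − 2 = 6.1.
- Planned total: placebo 26 × 1/1.3 = 20; drug 26 × 0.3/1.3 = 6. Rates: 20/940 = 2.13% and 6/940 = 0.64%. Gap: 14 events, or 14/940 = 1.49 points.

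**Effect on the overall SAE line.** The documents give no rate for SAEs other than COVID-19 events, so a placebo background *b* of 0.25% to 2% is an assumption. Let *e* be the endpoint-event rate in an arm and *R* the true ratio of other SAEs, drug to placebo. Taking the two kinds of event as independent:

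- placebo total = 1 − (1 − b)(1 − e_placebo)
- drug total = 1 − (1 − R·b)(1 − e_drug)

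Example, b = 0.5% and R = 2: placebo 1 − 0.995 × 0.97872 = 2.62%; drug 1 − 0.990 × 0.99362 = 1.63%; ratio 0.62.

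| Assumed background on placebo | Total SAE ratio if other SAEs double | Total SAE ratio if they triple |
|---|---|---|
| 0.25% | 0.48 | 0.58 |
| 0.5% | 0.62 | 0.81 |
| 1% | 0.85 | 1.17 |
| 2% | 1.13 | 1.62 |

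A table without the COVID-19 events would show 2.0 and 3.0 throughout. Ignoring the small product term, the arms are level when b(R − 1) = 1.49 points. That is a background of about 1.5% for a doubling and 0.75% for a tripling. Below those values the total favours the drug; above them it does not.

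**Do the two definitions pick out the same admissions?** Not exactly. For the efficacy endpoint, Protocol 8.1.2 says: "Hospitalization is defined as >24 hours of acute care, in a hospital or similar acute care facility". The SAE text in 10.3.2 refers to admission that usually includes an overnight stay. The endpoint runs to Day 28 and the AE summary to Day 34.

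**The case against.** The strongest reply is that the conflict is implied, not stated. Section 8.3.7 does not mention hospitalisation, and marking it not applicable may mean only that no list of exempt events was added and Appendix 3 governs. Appendix 3 then leans towards recording: the exemption falls away when progression is more severe than expected, and exclusion criterion 4 removes anyone needing or expected to need admission within 48 hours, so an admission may often meet that exception. This stands in part. It makes inclusion likelier, but leaves it to judgement, and the likelier inclusion is, the more the overlap matters.

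The second reply is that safety does not rest on one line. TEAEs are tabulated by SOC and PT, AEs are listed individually (SAP 5.2), AESIs are prespecified (SAP Appendix 5), every event gets a causality assessment, and the E-DMC reviews unblinded safety data and all deaths (Protocol 10.1.5.1). Standard safety tables under SAP 6.6 may show more, though their content is not stated. This also stands, and it confines the masking to the overall SAE line. None of these is a specified between-arm SAE comparison free of the efficacy events.

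Three stronger readings are tempting but not supported:

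- A reader might infer that COVID-19 admissions are SAEs under the protocol. The text supports only that they can be recorded as such.
- A reader might infer that drug harm as a whole would be hidden. The safeguards above argue against that.
- A reader might infer that these admissions necessarily feed AEs leading to discontinuation. Section 7.1 lists hospitalisation separately from AE and SAE, and dosing ends by Day 5 or 6, so overlap is possible, only for early admissions, and cannot be quantified from the documents.

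**Conclusion.** The point holds as a gap in both the recording rule and the SAE summary. The plan does not settle whether COVID-19 admissions are SAEs and specifies no SAE comparison without them. The planned efficacy effect would put about 14 more events on placebo, 1.5 points of about 940 per arm.

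That figure is a worst case. It assumes that all 26 events are recorded as SAEs, that the 70% reduction is realised, and that the endpoint events, which include death from any cause, are all COVID-19-related. It is not an expected distortion. How far it would mask a real excess depends on a background rate the documents do not give: at an assumed 0.5% or 1% a doubling of other SAEs would still look favourable to the drug, while at 2% it would not. No sample size, power or alpha figure is affected. The point is worth correcting because SAE incidence is a named secondary endpoint.

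**What to change.** 1. Reconcile Protocol 8.3.7, 10.3.1 and 10.3.2 so that one rule says how COVID-19 progression, including admission, is recorded. The rule should state which hospitalisation definition applies (8.1.2 or 10.3.2).
2. In SAP 6.2.2 and 6.6.1, present SAEs by arm both in total and excluding COVID-19-related hospitalisations and COVID-19-related deaths, by SOC and PT, through Day 34. Do the same for AEs leading to discontinuation where the events overlap.
3. Keep all other deaths in the second table. Excluding everything counted in the key secondary endpoint would be wrong, because that endpoint includes death from any cause and the exclusion could remove a drug-caused death.

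The cost is one protocol clarification and two extra tables. SAP 6.2.7 and 6.2.10 already use CRF data on hospitalisation due to COVID-19, so that flag exists. The downside is reliance on the COVID-19-relatedness classification. For deaths the efficacy endpoint does not need that classification, so it should be assigned without knowledge of treatment arm. Admissions on Days 29 to 34 and stays of 24 hours or less fall outside the efficacy definition, so the rule must say how they are treated.
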